Study NV20234 is a double-blind, randomized, stratified multi-center trial of conventional and double dose oseltamivir in immuno-compromised (IC) patients. The conventional dose in adults (≥ 18 years of age) and adolescents (from ≥ 13 to < 18 years of age) is 75 mg twice daily (BID) for 10 days. In children (from 1 to < 13 years of age) the conventional doses are 30, 45, or 60 mg BID for 10 days based on body weight. Immunocompromised (IC) patients who develop an influenza-like illness with confirmed influenza from a positive rapid diagnostic test, PCR, or viral culture will be enrolled during the influenza season. Patients will be stratified by:

- Transplant type: hematopoietic stem cell transplant [HSCT] vs. solid organ transplant [SOT] (Protocol Version A and B) or transplant status yes vs. no (Protocol Version C onwards).
- The time between onset of influenza symptoms and treatment start (up to 48 hours) (≤ 24 hours vs. > 24 hours) (Protocol Version A and B) or the time between onset of influenza symptoms and treatment start (up to 96 hours) (≤ 48 hours vs. > 48 hours) (Protocol Version C onwards).
- Influenza vaccination status for current influenza season (yes vs. no).
- Age (≤ 12 years vs. > 12 years).

See section 4.4.5 for further description of subgroup analyses.

2.1 **PROTOCOL SYNOPSIS**

The Protocol Synopsis is in [Appendix 1](#). For additional details, see the Schedule of Assessments in [Appendix 2](#).

2.2 **OUTCOME MEASURES**

All endpoints (safety, resistance, efficacy and PK) are defined in the SAP (descriptions of the endpoints are in Section 2 and the statistical methods used to describe the endpoints are described in Section 4). There are two co-primary endpoints – safety/tolerability and resistance. It is worth noting that the primary endpoint of this study changed during the course of the study. ‘Time to Resolution of All Influenza Symptoms’ was the primary endpoint in versions A

and B of the protocol. However, this endpoint was relegated to a secondary endpoint to reflect the change in objectives introduced in Protocol Version C.

Baseline is defined for all endpoints as the pre-dose reading on Day 1.

2.2.1 Primary Efficacy Outcome Measures

Not applicable as efficacy is not the primary objective.

2.2.2 Secondary Efficacy Outcome Measures

Secondary efficacy outcome measures are defined below.

- Area Under the Effect-Time Curve (AUE) for all symptoms (adults only). This will be calculated from baseline (symptom score prior to start of study drug or, if missing, before 12 h after starting treatment) to the time at which all symptoms are first alleviated, i.e. ≤ 1 . Totals scores will be tracked over time. The AUE of these average scores is then calculated for each subject using the trapezoidal rule. The median of those AUE will be compared between groups using CI.
- TTR of Individual Symptoms (all patients with baseline symptom scores > 1) is defined as the time from treatment initiation to the start of the 24 hour period at which a specific symptom score is ≤ 1 and remains ≤ 1 for at least 21.5 hours. For children, if a score of 4 (“do not know” or “not applicable”) occurs at any assessment during the study for any given symptom(s), the assessment will not be included in calculating the TTR. Patients with symptom scores ≤ 1 at baseline which remain ≤ 1 for at least 21.5 hours thereafter will have a TTR set to missing. Patients with symptom scores > 1 at baseline followed immediately by scores ≤ 1 for at least 21.5 hours will have a TTR set to zero.
- The AUE for Individual symptoms (adults only) will be calculated from baseline (symptom score prior to start of study drug) to the time at which the individual symptom is first alleviated (≤ 1). The AUE of the individual symptom score is calculated for each subject using the trapezoidal rule.
- Time to resolution of fever is defined as the time from treatment initiation to the last time at which temperature was $\geq 37.8^\circ\text{C}$ (all patients). For patients who did not have a temperature $\geq 37.8^\circ\text{C}$ at baseline and throughout the dosing period, the time to resolution of fever will be missing. For patients who had a temperature of $\geq 37.8^\circ\text{C}$ at baseline, followed immediately by a temperature of $< 37.8^\circ\text{C}$ at their first post-baseline assessment, the time to resolution of fever will be zero. Patients who still had a temperature $\geq 37.8^\circ\text{C}$ at the end of the follow-up period will be censored at that time point. Patients who withdraw prior to resolution of fever will be censored at the time of withdrawal.

Note: As the introduction of the electronic diary removed the requirement for the patient to record their own baseline temperature, the baseline for these patients will be defined as the temperature recording collected at the first site visit. It is recognized that the absence of a true patient recorded temperature, using the same thermometer and body site, will limit interpretation of this endpoint.

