2.2.2.2 Viral load

Viral load is the number of viral particles per mL of blood. It is reported in \log_{10} scale and expressed in 1) virus particles/mL (\log_{10} vp/mL) calculated from the quantitative RT-PCR assay (reverse transcriptase polymerase chain reaction) and 2) 50% tissue culture infectious dose (\log_{10} TCID₅₀) obtained after viral culture.

- Viral load change from baseline over time expressed in \log_{10} vp/mL, where baseline is defined as the pre-dose day 1 result.
- Viral load change from baseline over time expressed in \log_{10} TCID₅₀/mL, where baseline is defined as pre-dose day 1 result. \log_{10} TCID₅₀/mL is calculated as: $TCID_{50} = -\left(X_0 - d/2 + d \sum_{x=p=1}^{x_{min}} p_x\right)$, (Ramakrishnan MA, 2016) where:

X_0 = positive logarithm of the highest dilution at which all quadruplicate wells are positive in the haemagglutination assay or NP-ELISA,

$p_x = \frac{r_x}{4}$, where r_x is the number of positive wells (out of 4) at dilution x ,

$x_{p=1}$ is maximum dilution at which all 4 wells are positive,

x_{min} is the dilution at which all four wells are negative for the first time, and

d is the \log_{10} dilution factor, i.e. $\log_{10}10^{-1} = -1$.

N.B. The data contains two variables: X_0 and X_1 , where $X_1 = -\sum_{x=p=1}^{x_{min}} p_x$ and $X_0 = -X_0$ (see above). Thus, programmatically,

$$TCID_{50} = X_0 - 0.5 + 0.25X_1$$

- Area under the viral titer curve calculated applying the trapezoidal rule to the \log_{10} TCID₅₀/mL viral load titer.
- Area under the viral titer curve calculated applying the trapezoidal rule to the \log_{10} vp/mL viral load titer.
- Peak viral titer per arm defined as the maximum \log_{10} TCID₅₀/mL.
- Peak viral titer per arm defined as the maximum \log_{10} vp/mL.

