2.2.2.3 Viral shedding

Time to cessation of viral shedding is defined as the time from treatment initiation to the time of first negative result with no subsequent positive results. Event is applicable only to patients infected at baseline. A value of 0.5 or less \log_{10} TCID₅₀/mL and a value of 0.26 or less \log_{10} vp/mL for Flu A strains and 0.3 or less \log_{10} vp/mL for Flu B strains will be interpreted as a negative result. Any subsequent missing values for either RT-PCR or culture will be assumed to be negative. Patients who did not have the right assay to determine viral shedding (Haemagglutination assay or NP-ELISA) will be excluded from this analysis.

- Time to cessation of viral shedding determined by Haemagglutination assay for H1N1 and Flu B strains or NP ELISA (NucleoProtein Enzyme-Linked Immunosorbent Assay) for H3N2 strains after viral culture and expressed in \log_{10} TCID₅₀/mL (50% Tissue Culture Infectious Dose).
- Time to cessation of viral shedding determined by RT-PCR and expressed in \log_{10} virus particles/mL (vp/mL).
- Incidence of patients with viral shedding by RT-PCR by visit.
- Incidence of patients with viral shedding by viral culture by visit.

- Incidence of persistent shedding, defined as $<1 \log_{10}$ vp/mL reduction at end of treatment, compared with baseline.

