4.4.4.4 Comparison of TTR of All Symptoms to Historical Control

The following Kaplan-Meier analyses will be carried out using the mITTi population to support the comparison of Study NV20234 treatment response with the historical placebo response with both 1:1 and 1:>1 ratios:

- The TTR of all symptoms for adults using only follow-up symptom data recorded up to and including 25 days compared with historical placebo data. This is to investigate the impact of differences in the follow-up observation periods between study NV20234 and the oseltamivir treatment database. Adult patients in Study NV20234 who have not experienced resolution of symptoms by day 25 will be censored on day 25. In the historical studies (see section 4.4.2.2 above and [appendix 4](#)) the final assessment was between days 17 and 25 post onset. A sensitivity analysis will be carried out comparing results from the previous analyses against an analysis without censoring at 25 days, i.e. using the current final assessment ~40 days after onset of symptoms.
- The TTR of all symptoms for patients who had symptoms onset ≤ 48 hours before first dose, for each active treatment group and combined, compared with matched historical control patients.

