TTR fever	Kaplan-Meier	Treatment median [90% CI] Responses for : NV20234 conventional, NV20234 double, NV20234 pooled, historical treatment conventional, historical treatment double, historical placebo for conventional, historical placebo for double, historical placebo for pooled.	mITTi	Benchmarking plot**	1) Overall 2) Age cohort (>= 18 Y, < 18 Y) All CI's on one plot but also split by a) pooled b) conventional c) double	g_km_t1_t2_hist plac_treat_RES F_MITI_AD_90 g_km_t1&2_hist plac_treat_RES F_MITI_AD_90 Repeated 1:1 and 1:>1 matches
AUC total symptom scores	Median, IQR	Treatment Responses by treatment arms	mITTi, ITT, ITTi	Dose-Response main summary for this endpoint	Adults only	g_auc_ALLEVA S_AD t_auc_ALLEVAS AD
AUC total symptom scores	Median, IQR	Treatment median [IQR] for: NV20234 conventional, NV20234 double, NV20234 pooled, historical treatment conventional, historical treatment double, historical placebo for conventional, historical placebo for double, historical placebo for pooled.	mITTi	Benchmarking plot	For adults only : All plots on one plot but also split by a) pooled b) conventional dose c) double dose	g_km_t1_t2_hist plac_treat_AUC ALLEVAS_MITI_ AD_90 g_km_t1&2_hist plac_treat_ALLE VAS_MITI_AD_ 90 Repeated 1:1 and 1:>1 matches
AUC individual symptom score	Median, IQR	Treatment Responses by treatment arm	mITTi	Dose-Response main summary for this endpoint	Adults	g_auc_ALLEVIS _AD t_auc_ALLEVIS _AD
AUC viral titer	Median, IQR	Treatment Responses by treatment arm	mITTi	Dose-Response main summary for this endpoint	Adults Children	g_ef_auc_AUCC LT_MITI_AD t_ef_auc_AUCC LT_MITI_AD

						t_ef_auc_AUCC LT_MITI_CH t_ef_auc_AUCP CR_MITI_CH t_ef_auc_AUCP CR_MITI_CH
AUC viral titer	Plot Median, IQR	Treatment median [IQR] Responses for: NV20234 conventional, NV20234 double, NV20234 pooled, historical treatment conventional, historical treatment double, historical placebo for conventional, historical placebo for double, historical placebo for pooled.	mITTi	Benchmarking plot	All plots on one plot but also split by a) pooled b) conventional c) double	g_km_t1_t2_hist plac_treat_AUC CLT_MITI_AD_90 g_km_t1&2_hist plac_treat_AUCCLT _MITI_AD_90 Repeated 1:1 and 1:>1 matches
Peak viral titer	Median, IQR	Treatment Responses by treatment arms	mITTi, ITT, ITTi	Dose-Response main summary for this endpoint	a) Adults b) Children	t_ef_auc_PEAK CLT_MITI_AD t_ef_auc_PEAK CLT_MITI_PE t_ef_auc_PEAK PCR_MITI_AD t_ef_auc_PEAK PCR_MITI_PE

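### The historical benchmarks for fever and viral shedding compare about 40 days of follow-up with 17 to 25 days, using definitions that lengthen with follow-up; only symptom resolution gets a 25-day cut

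*SAP*

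**What the plan says.** **Follow-up.** Section 4.4.4.4 plans an analysis of time to resolution of all symptoms in adults "using only follow-up symptom data recorded up to and including 25 days compared with historical placebo data". The stated purpose is "to investigate the impact of differences in the follow-up observation periods between study NV20234 and the oseltamivir treatment database". In the historical studies "the final assessment was between days 17 and 25 post onset"; the uncut version is run "using the current final assessment ~40 days after onset of symptoms". In Table A5.1 the only output restricted to 25 days is for resolution of all symptoms.

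**Definitions.**
- Symptoms (section 2.2.2.1): first resolution held for at least 21.5 hours, with later relapses ignored.
- Fever (section 2.2.2.1): "Time to resolution of fever is defined as the time from treatment initiation to the last time at which temperature was" at or above 37.8°C, censored at the end of follow-up if still febrile. The time is zero if a febrile baseline is followed at once by a reading below 37.8°C.
- Shedding (section 2.2.2.3): time to "the time of first negative result with no subsequent positive results". Later missing values count as negative.
- Viral AUC (section 2.2.2.2): "Area under the viral titer curve calculated applying the trapezoidal rule to the" log10 titre. No end time is given, nor the value a negative takes in the integral.

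**Benchmarks.** Table A5.1 plans historical benchmarking plots for cessation of shedding, fever and viral-titre AUC, with 1:1 and 1:>1 matches. The groups plotted beside the trial's own arms include "historical treatment conventional, historical treatment double, historical placebo for conventional". None of these rows has a 25-day version.

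**The concern.** Longer follow-up alone does not bias a Kaplan-Meier median when the endpoint is a first event; patients followed for less time are simply censored earlier. It matters when the endpoint is the last occurrence of something, or is undone by a later positive, because each extra day of observation is another chance to extend the duration. Fever and shedding are of that kind and symptom resolution is not. The plan therefore protects the endpoint that needs it least and leaves the two exposed endpoints uncut.

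These plots help readers judge whether treated immunocompromised patients do better than untreated historical patients, which section 4.4.2.2 gives as the reason for the historical comparison. A duration lengthened by a reading that the controls had no opportunity to give would count against oseltamivir in this population for a reason unrelated to the drug.

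**Working it through.** There is no stated SAP figure to reproduce on this point. The check sets the definitions against the observation windows, then illustrates the size under declared assumptions.

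**1. Windows (Appendix 2 and section 4.4.4.4).** Diary temperatures are recorded twice daily on Days 1-10 and once daily thereafter. Swabs are scheduled on Days 1, 2 or 3, 6, 8, 11, 15 and 40. Historical patients have their final assessment on days 17-25 post onset.

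| Endpoint | Ends at | Can a reading after the controls' window change it? | 25-day version? |
|---|---|---|---|
| All symptoms | first resolution | not once resolved | yes |
| Fever | last reading ≥37.8°C | yes, any late diary reading | no |
| Shedding | negative with no later positive | yes, the Day 40 swab | no |
| Viral AUC | not stated | depends on the end time used | no |

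**2. Fever, illustrated.** Assumptions, none of them in the SAP: exponential time to first fever resolution with a 72 h median; from day 5, an independent daily chance r of a reading ≥37.8°C; the same true course in both sources; windows counted from treatment start. If F is the distribution of first resolution and k the number of days in the window after time t on which a late fever can occur, the median solves

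F(t) × (1 − r)^k = 0.5, with F(t) = 1 − 2^(−t/72).

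Example, r = 0.5%:
- 25-day window: k = 21 (days 5-25), 0.995^21 = 0.900, F(t) = 0.5/0.900 = 0.555, t ≈ 84 h.
- 40-day window: k = 36 (days 5-40), 0.995^36 = 0.835, F(t) = 0.5/0.835 = 0.599, t ≈ 95 h.

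Simulated medians (400,000 patients) agree with this formula:

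| r per day | 17 days | 25 days | 40 days | 40 minus 25 | 40 minus 17 |
|---|---|---|---|---|---|
| 0 | 72.1 h | 72.1 h | 72.1 h | 0 h | 0 h |
| 0.5% | 79.4 h | 84.5 h | 94.9 h | 10.4 h | 15.5 h |
| 1% | 88.0 h | 100.2 h | 128.8 h | 28.6 h | 40.8 h |

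The chance of at least one such reading in days 26-40 is 1 − (1 − r)^15, that is 7.2% at r = 0.5% and 14.0% at r = 1%. For scale only, section 2.3 uses 34 h as the clinically relevant difference for symptom resolution, a different endpoint. The zero-time rule is not modelled and would reduce these shifts. With one common cut-off the artefact is zero by construction when the true course is the same.

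**3. Shedding, illustrated.** No swab is scheduled between Days 15 and 40, so the excess over a 25-day window rests on the Day 40 swab. If a share q is positive there after an earlier negative, the median moves to the 0.5/(1 − q) quantile of the original distribution: 0.526, 0.556 and 0.625 for q = 5%, 10% and 20%. For an assumed exponential course with a 6.0-day median, that is 6.5, 7.0 and 8.5 days.

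**4. Viral AUC, only if it is carried to Day 40.** Take an assumed profile with values 5, 4.5, 2.5, 1.5, 0.5, 0.5, 0.5 log10 at Days 1, 2.5, 6, 8, 11, 15, 40. Its AUC is 33.375 log10·days to Day 25. Days 25-40 add 0.5 × 15 = 7.5, giving 40.875, a ratio of 1.22. With negatives coded 0 and the patient clear by Day 11, the ratio is 1.00. A patient at 2.0 on Day 15 falling to 0 on Day 40 goes from 64.25 to 73.25, a ratio of 1.14. The answer turns on two choices the SAP does not state.

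**The case against.** These are secondary, descriptive plots with no hypothesis test (section 4.4), and section 4.4.4.3 calls historical work on other endpoints potential and exploratory. The note to the fever definition already warns of limited interpretation, though for thermometer and body-site reasons and not follow-up. The zero-time rule shields some fever patients, but it sits awkwardly with the last-reading definition if fever returns. The shedding effect rests on one swab, and a missing later value counts as negative. All of this limits the weight and the size. It does not remove the mismatch, which the SAP itself thought worth examining for symptoms.

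Several stronger readings are tempting and are not supported:
- **That the size of the bias is known, or that observation length alone explains any difference.** The SAP gives no recurrence rates. It does not say how the historical fever and shedding variables were derived, or when the last historical swab or temperature was taken. Section 4.4.2.2 also concedes that immune status and drug effect cannot be separated.
- **That every later fever is excess.** Controls can have later fevers within their own window; only those after it create the artefact.
- **That the viral AUC runs to Day 40 and mainly reflects the period after treatment.** No end time is stated. A control followed to day 25 would also accrue part of any area after Day 15.
- **That the randomised dose comparison is biased too.** Both arms share one visit schedule, so unequal follow-up between sources does not touch it.

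**Conclusion.** The point holds for the historical benchmarks of fever and cessation of shedding. Follow-up is acknowledged to be unequal, both definitions let later readings lengthen the outcome, and no cut is planned. The direction is against this trial's arms. The true size cannot be calculated from the SAP. Under the assumptions in the working (72 h base, independent daily recurrence, same true course), the fever median shifts by about 0, 10 or 29 h between a 25-day and a 40-day window at 0, 0.5 or 1% per day; the zero-time rule would reduce this.

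For viral-titre AUC the finding is narrower: the end time and the coding of negatives are unspecified, so the benchmark may integrate over unequal windows. The symptom-score AUE stops at first alleviation and is not affected. The point is worth correcting because it is cheap; it does not bear on the co-primary safety and resistance endpoints.

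**What to change.** For the Appendix 5 historical benchmarks:

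1. **Fever and shedding.** Truncate this trial's temperatures and swabs at the matched control's last assessment, or at the 25-day limit of section 4.4.4.4, and censor there. State whether days count from symptom onset or from first dose. For swabs, a 25-day cut means using data to Day 15, as none is scheduled between Days 15 and 40.
2. **Viral-titre AUC.** Compute it over one fixed window observed in both sources, with the same stated value for negatives in each.
3. **Full-follow-up versions.** Keep them as supplementary outputs.
4. **Fever wording.** Say which rule governs when the first post-baseline reading is below 37.8°C and fever later returns.

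Make no change on this ground to the AUC window for the randomised dose comparison.

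The cost is SAP wording and a date cut in the derivation programs, with no new data. The downside is that late fever and late shedding drop out of the benchmark, though they stay visible in the full-follow-up and by-visit outputs.

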2.2.2.2 Viral load

Viral load is the number of viral particles per mL of blood. It is reported in \log_{10} scale and expressed in 1) virus particles/mL (\log_{10} vp/mL) calculated from the quantitative RT-PCR assay (reverse transcriptase polymerase chain reaction) and 2) 50% tissue culture infectious dose (\log_{10} TCID₅₀) obtained after viral culture.

- Viral load change from baseline over time expressed in \log_{10} vp/mL, where baseline is defined as the pre-dose day 1 result.
- Viral load change from baseline over time expressed in \log_{10} TCID₅₀/mL, where baseline is defined as pre-dose day 1 result. \log_{10} TCID₅₀/mL is calculated as: $TCID_{50} = -\left(X_0 - d/2 + d \sum_{x=p=1}^{x_{min}} p_x\right)$, (Ramakrishnan MA, 2016) where:

X_0 = positive logarithm of the highest dilution at which all quadruplicate wells are positive in the haemagglutination assay or NP-ELISA,

$p_x = \frac{r_x}{4}$, where r_x is the number of positive wells (out of 4) at dilution x ,

$x_{p=1}$ is maximum dilution at which all 4 wells are positive,

x_{min} is the dilution at which all four wells are negative for the first time, and

d is the \log_{10} dilution factor, i.e. $\log_{10}10^{-1} = -1$.

N.B. The data contains two variables: X_0 and X_1 , where $X_1 = -\sum_{x=p=1}^{x_{min}} p_x$ and $X_0 = -X_0$ (see above). Thus, programmatically,

$$TCID_{50} = X_0 - 0.5 + 0.25X_1$$

- Area under the viral titer curve calculated applying the trapezoidal rule to the \log_{10} TCID₅₀/mL viral load titer.
- Area under the viral titer curve calculated applying the trapezoidal rule to the \log_{10} vp/mL viral load titer.
- Peak viral titer per arm defined as the maximum \log_{10} TCID₅₀/mL.
- Peak viral titer per arm defined as the maximum \log_{10} vp/mL.

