4.4 EFFICACY ANALYSIS

All efficacy endpoints are considered secondary or exploratory. As no formal efficacy hypothesis is being tested, treatment differences presented in any efficacy analyses will be reported with associated confidence intervals (CIs) only. Efficacy endpoints will be summarized by age group. All summaries and analyses are described below and listed in [Appendix 5](#). All efficacy analyses will be based on the mITTi and ITTi populations. ITT will be presented for the main efficacy TTR summary tables (all symptoms and temperature only) to investigate the effect of treatment in a “real world” scenario, i.e. unknown infection status and/or adherence. N.B. Regulatory bodies have asked for these outputs in pivotal studies.

All efficacy summaries and analyses will be carried out separately for adults (patients ≥ 18 years) and paediatrics (patients <13 years old). Adolescent data (patients aged between ≥ 13 and <18 years old) will be listed as appropriate.

As the symptom data are recorded on patient diaries, data errors cannot be queried. Obvious data errors, i.e. temperature 100°C , will be excluded and documented. For duplicated data, the worst evaluation will be used to obtain conservative estimates.

The endpoints as described in the protocol have been expanded to give sufficient information of the derivations required, e.g. *symptom scores* was the endpoint defined in the protocol but *Time To Resolution of symptom scores* is how it is described in the SAP.

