4.5 PHARMACOKINETIC AND PHARMACODYNAMIC ANALYSES

Individual and mean plasma concentrations from the oseltamivir population PK model at each sampling time-point for oseltamivir and oseltamivir carboxylate will be presented by listings and descriptive summary statistics, including means, geometric means, medians, ranges, standard deviations and coefficients of variation. Individual and mean concentration-versus-time profiles will be plotted on linear and semi-logarithmic scales.

Plasma concentration data from sparse sampling will be analysed by the clinical pharmacologist using an established population PK model to determine key exposure parameters defined in Section 2.2.4. Note: For IC children (≤ 12 years) and adolescents ($> 12 - \leq 17$ years), plasma oseltamivir and oseltamivir carboxylate concentrations will be modeled in NONMEM using a structure similar to a comprehensive population PK model which was previously developed using oseltamivir and oseltamivir carboxylate plasma concentration data from non-IC children and adults (ages 1 to 80 years).

The PK parameters will be listed and summarized by treatment group using descriptive summary statistics including means, geometric means, medians, ranges, standard deviations and coefficients of variation.

Exposure-response relationships will be presented in the CSR through the use of scatter plots, plotting each of the estimated PK parameters separately against the area under the viral titer curve; the peak viral titer, and the time to cessation of viral shedding. Different symbols will be used to differentiate treatment groups.

All listings and summaries of plasma concentrations and estimable PK parameters will be based on the PKEP population.

Further PK and PK/PD analyses may be carried out by the clinical pharmacology group. This will be reported in a separate report when appropriate.

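### The programming line for the culture titre (log10 TCID50) does not follow from the data-variable definitions given just above it

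*SAP*

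**What the plan says.** SAP section 2.2.2.2 gives the log10 TCID50 titre as -(X0 - d/2 + d·Σp_x). Its ingredients are:

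- X0 is the "positive logarithm of the highest dilution at which all quadruplicate wells are positive in the haemagglutination assay or NP-ELISA".
- d is the log10 dilution factor, -1.
- Each p_x is a proportion, namely a quarter of r_x, and r_x counts how many of the four wells were positive at that dilution. The sum runs from the last all-positive dilution to the first all-negative one.

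A note follows: "N.B. The data contains two variables". It defines the first as minus the formula's X0 and the second as X_1 = -Σp_x. It ends "and $X_0 = -X_0$ (see above). Thus, programmatically", and the line to be coded is "TCID_{50} = X_0 - 0.5 + 0.25X_1".

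Section 2.2.2.3 uses the resulting titre to classify cultures: "A value of 0.5 or less" on the log10 TCID50/mL scale is read as negative.

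**The concern.** The SAP presents the line as a consequence of the formula and the note. The 0.25 in the line looks like the conversion from a count of four wells to a proportion. However, the note says X_1 is already built from proportions, and with a minus sign. A programmer who trusts both the note and the line would then compute wrong titres.

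The titre feeds several secondary culture endpoints: change from baseline (also listed in section 4.8), area under the culture titre curve, peak culture titre, culture shedding by visit, and time to cessation of shedding by culture. The exposure-response plots in section 4.5 against the "area under the viral titer curve; the peak viral titer, and the time to cessation of viral shedding" are affected so far as they use culture results.

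There is a separate sign problem in the formula. Calling X0 a positive logarithm does not fit d = -1 and the outer minus. In addition, the same symbol, X_0, stands for two quantities of opposite sign.

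**Working it through.** To keep the symbols apart, X0 below is the formula's symbol, and V0 and V1 are the two data variables (the SAP's X_0 and X_1 in the note and the line). Write S = Σp_x and R = Σr_x, so S = R/4. Let 10^-k be the last dilution with all four wells positive. Because the sum starts there, S is at least 1.

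**Step 1: the formula with d = -1.**
-(X0 - d/2 + d·S) = -(X0 + 0.5 - S) = -X0 - 0.5 + S.

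**Step 2: substitute the note's definitions, V0 = -X0 and V1 = -S.**
The result is V0 - 0.5 - V1. The SAP's line is V0 - 0.5 + 0.25·V1. The first two terms agree. The coefficient of V1 should be -1 and is +0.25.

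Changing signs cannot repair this. Under any sign convention the formula's coefficient of S is +1 or -1, while the line with V1 = S or -S gives +0.25 or -0.25. The line matches the formula only if V1 = +R, because 0.25·R = S.

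**Step 3: the sign of X0.**
Plate 1 has 4/4 wells positive at 10^-3, 2/4 at 10^-4 and 0/4 at 10^-5, so k = 3, R = 6 and S = 1.5. The 50% endpoint is at 10^-4, so the titre is 4.0.

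- X0 = -3 (signed log10 dilution): -(-3 + 0.5 - 1.5) = 4.0.
- X0 = +3 (positive logarithm, as the definition says): -(3 + 0.5 - 1.5) = -2.0.

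The formula therefore needs the signed logarithm. With that reading V0 = -X0 = +k, and the correct titre is k - 0.5 + S.

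**Step 4: what the printed line returns, with V0 = +k.**
Plate 2 has 4/4 at 10^-1 and 0/4 at 10^-2, so k = 1, R = 4, S = 1 and the correct titre is 1 - 0.5 + 1 = 1.5.

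| V1 in the file | Plate 1 | Plate 2 | Change, plate 1 to 2 | Titre too low by |
|---|---|---|---|---|
| Correct titre | 4.0 | 1.5 | -2.5 | – |
| R | 3 - 0.5 + 1.5 = 4.0 | 1.5 | -2.5 | 0 |
| -R | 3 - 0.5 - 1.5 = 1.0 | -0.5 | -1.5 | 2·S |
| S | 3 - 0.5 + 0.375 = 2.875 | 0.75 | -2.125 | 0.75·S |
| -S (the note's definition) | 3 - 0.5 - 0.375 = 2.125 | 0.25 | -1.875 | 1.25·S |

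Since S is at least 1, the last row is at least 1.25 log10 too low. In the rows for -R and -S, plate 2 falls below the 0.5 cut-off and is read as negative. The error is a multiple of S, so it cancels in change from baseline only when both plates have the same S.

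**Step 5: every definition taken literally.**
If X0 is also a positive logarithm, V0 = -k. Plate 1 then gives -3 - 0.5 - 0.375 = -3.875. In general the line gives -k - 0.5 - 0.25·S, which for k ≥ 0 and S ≥ 1 never exceeds -0.75. Every culture would be read as negative.

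**The case against.** The best counter-argument is that the line is right and only the note is mis-transcribed. The factor 0.25 makes sense only for a count of wells, the note's definition of V0 does carry the formula into the line's first two terms, and with V0 = +k and V1 = R the line gives the correct titre. On that reading no result changes. This is a fair inference, but nothing in the SAP confirms it: the note says explicitly what the data contain, and it says something else.

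Second, a symbol may have been lost when the PDF was converted to text; the summation limit appears in two forms. A lost minus on V1 alone would not help, because V1 = S still gives 2.875 instead of 4.0. Two misreadings would be needed, the minus and p for r, and the positive-logarithm problem would remain.

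Third, the fully literal reading fails so visibly that it would probably be noticed. That is plausible, but the partly literal readings in the table give believable titres and would be harder to spot.

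Fourth, the reach is limited. The RT-PCR endpoints and the co-primary safety and resistance endpoints do not use this titre, and section 4.4 states "As no formal efficacy hypothesis is being tested". This stands and limits the severity.

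**Conclusion.** The concern holds. As written, the note's definition of X_1 and the programming line are incompatible: the sign is opposite and the division by 4 is applied twice. Which of the two is wrong cannot be settled from the SAP.

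The size depends on the laboratory file. With X_0 = +k, the error is zero if X_1 is the count of positive wells and at least 1.25 log10 if X_1 is as the note defines it. In the latter case a plate with a titre of 1.5 would be classed as negative. These plates illustrate the algebra; they do not estimate the effect on trial results. The point should be fixed before programming, and it concerns secondary culture endpoints only.

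**What to change.** 1. In section 2.2.2.2, define X0 as the signed log10 of the dilution (10^-3 gives -3) with d = -1, and delete the word positive.
2. Give the two data variables names that differ from the formula's symbols.
3. Before programming, check the sign and units of both variables in the laboratory file. With the first variable equal to +k (if the file holds -k, reverse its sign first), use the matching line, in the SAP's present names:
   - X_1 = Σr_x: keep X_0 - 0.5 + 0.25·X_1 and correct the note.
   - X_1 = -Σr_x: X_0 - 0.5 - 0.25·X_1, and correct the note.
   - X_1 = Σp_x: X_0 - 0.5 + X_1, and correct the note.
   - X_1 = -Σp_x: X_0 - 0.5 - X_1; the note's definition of X_1 stands.

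   Each line reduces to k - 0.5 + Σp_x.
4. Add plate 1 as a program check: 4/4 at 10^-3, 2/4 at 10^-4 and 0/4 at 10^-5 must return 4.0.

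The cost is a corrected definition or line in the SAP, plus a check of two variables.
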